#### 1.6.5 PERCUTANEOUS PULMONARY ARTERY THROMBOEMBOLECTOMY

Interest in percutaneous pulmonary artery thromboembolectomy flourished on a clinical landscape of effective but relatively slow thrombolytic treatment of PE and risk of thrombolytic-related bleeding complications even when drugs were administered with a lower-dose, catheter-directed approach. Direct pulmonary arterial thromboembolectomy offered the opportunity for rapid removal of thrombus while limiting hemorrhagic, thrombolytic-related complications in those cases where thrombectomy could be utilized as a sole therapy, without pharmacologic thrombolysis.

Historically, percutaneous thromboembolectomy for PE predated catheter-directed thrombolysis. The therapy began with the Greenfield suction catheter, first reported in 1969. After that, other technologies were attempted, including fragmentation of proximal emboli, rheolytic thrombectomy, and the use of various pulmonary artery thromboembolectomy devices. To the extent that the percutaneous thromboembolectomy devices removed obstructing thromboembolism without the need for thrombolytic therapy, such devices presented the potential for normalization of pulmonary arterial flow without the hemorrhagic complications associated with thrombolytic agents. This is the rationale for FlowTriever as it has the advantages of a percutaneous procedure, with expectation that the bleeding complications of thrombolysis will be minimized.

#### 1.6.6 LIMITATIONS OF CURRENTLY APPROVED THERAPY

Generally, the guidelines agree that the mainstay of treatment for massive and submassive PE is anticoagulation and that thrombolysis should be offered to unstable patients. 4, 15, 61 They further suggest that thrombolytics not be routinely used to treat submassive PE but should instead be considered on a per patient basis. The benefit of thrombolysis for patients with submassive PE is not clear and treatment may cause more harm than benefit for many patients; lytic therapy must be weighed against the risk of major bleeding, including the risk of intracranial hemorrhage.

FLARE-FT2 Study Page 15 of 60 **CONFIDENTIAL** 

The goal of a successful interventional procedure is to restore RV outflow through the pulmonary artery, thereby disrupting the potentially lethal cascade towards hemodynamic collapse. There is a strong clinical need to develop a reliable, rapid, percutaneous method of clot removal for the treatment of clinically significant acute PE. The need is especially strong for a mechanical method that does not rely on the use of thrombolytics, as physicians are reluctant to administer lytics given the high bleeding risk and because manypatients cannot tolerate lytics. The FlowTriever System was developed to meet this need to rapidly restore blood flow through the pulmonary vasculature in patients experiencing acute submassive pulmonary embolism. Once the immediate clot burden is removed, the blood flow is restored and the acute physiological effects from pressure overload should begin to dissipate.

The FlowTriever System including use of the FlowTriever Catheter was designed to remove emboli and restore blood flow through the pulmonary arteries. The goal in using this device is not 100% removal of clot, but rather to remove enough clot to make a clinically significant difference in the patient by reducing the patient's risk level for further complications and enable the endogenous thrombolysis mechanism to further reduce any residual clot. Should there be anyresidual or distal clot that is not part of the immediate emergent issue it should be treated according to the medical judgment of the Investigator on a case-by-case basis.

# 2 INVESTIGATIONAL DEVICE

# 2.1 DEVICE DESCRIPTION

The FlowTriever Retrieval/Aspiration System ("FlowTriever System") is comprised of the FlowTriever2 Catheter and Triever Catheter.

# 2.2 OPERATING PRINCIPLE

The FlowTriever2 Catheter provides a mechanical means for the retrieval of blood clots, which can then be aspirated using the Triever Catheter, from the vasculature. These features facilitate the reperfusion of vasculature obstructed by acute clot.

The system is designed for use with a 0.035" guidewire. The outside diameter of the Triever Catheter is available in 16 Fr, 20 Fr, and 24 Fr sizes. The outside diameter of the FlowTriever2 Catheter is 17 mm.

An introducer sheath is used to access the appropriate vessel and place the 0.035" guidewire through and past the clot under fluoroscopic guidance. The Triever Catheter with dilator is then introduced over the guidewire and situated on the proximal side of the clot. The tip of the dilator and Triever Catheter contain radiopaque markers for fluoroscopic positioning. The dilator is removed from the Triever Catheter, and the FlowTriever2 Catheter is placed over the guidewire, through the Triever Catheter, and is passed through the clot. The delivery catheter component of the FlowTriever2 Catheter is retracted, causing the self-expanding wireform component of the FlowTriever2 Catheter to expand within the blood vessel distal to, and within, some portion of the clot. Expansion of the device may allow some blood flow to be restored. The proximal end of the self-expanding wireform contains a radiopaque marker to aid in maintaining proper position. The FlowTriever2 Catheter can be manually retracted into the Triever Catheter, and simultaneous aspiration of fluid and clot can be performed through the Triever Catheter using a provided large-bore syringe. The device with captured clot is removed from the body.

[figure not shown]
Pulmonary embolisms are caused by clots that typically originate in the leg in the form of a cast of the vessel from which they broke loose. The clots tend not to be the same diameter of the pulmonary artery. They travel en masse and often fold upon themselves, and/or collect together in the pulmonary artery, giving the appearance of a large clot. Retrieving the clot is similar to grabbing the head of the snake and pulling in the rest of the clot (body) as with retraction and aspiration. The elasticity of the clot, depending on its age, and various other factors, make it soft enough to deform during the retrieval process and fit into the Triever Catheter.

# 2.3 DEVICE CONSTRUCTION/OPERATION

FlowTriever2 Catheter

The FlowTriever2 Catheter is comprised of a FlowTriever2 Catheter, delivery catheter, a hemostasis valve Y connector and one-way stopcock. The FlowTriever2 Catheter is preloaded into the delivery catheter and provided to the user in an assembled state (Figure 3.1).

Figure 3.1: FlowTriever2 Catheter

The outer diameter of the FlowTriever2 Catheter is 17 mm. The FlowTriever2 Catheter shaft is fabricated from stainless steel, Pebax, and PTFE/FEP/polyimide blend. Radiopaque platinum marker bands are positioned at the proximal end of the FT2 element to aid with fluoroscopic visualization (Figure 3.2).

[figure not shown]
[figure not shown]

Figure 3.2 FlowTriever2 Catheter Model, Sizes and Dimensions

The delivery catheter is a single lumen catheter comprised of a stainless-steel braid reinforced Pebax shaft with a polyethylene terephthalate (PTFE) liner with a proximal Luer fitting to connect to a "Y" connector with a rotatable hemostatic valve and stopcock. A radiopaque platinum marker is positioned near the distal tip to aid with fluoroscopic visualization (Figure 3.3).

[figure not shown]
Figure 3.3: Delivery Catheter

# Triever Catheter

The single-lumen Triever Catheter is available in three sizes: 16F, 20F, and 24F. The Triever Catheter and dilator are introduced together over a previously placed 0.035" exchange length guidewire (not provided). The Triever Catheter shaft is constructed from Pebax embedded with a stainless-steel coil and braid to prevent lumen collapse and provide flexibility, pushability, and strength. The shaft lumen is lined with PTFE. There is a Pebax/silicone hemostasis valve with a side-port terminating in a stopcock bonded to the proximal end of the Triever Catheter shaft. The dilator is constructed of low-density polyethylene (LDPE) with a Luer fitting at the proximal end to accommodate a "Y" connector with a rotatable hemostatic valve and stopcock. The dilator is compatible with the 0.035" guidewire and is provided to facilitate Triever Catheter advancement. The tip of the dilator is radiopaque, and a radiopaque platinum marker is positioned near the distal tip of the Triever Catheter to aid with fluoroscopic visualization. A large-bore, 60 cc VacLok Vacuum Syringe is used to aspirate clot from the Triever Catheter. The syringe is fitted with a quick-release connector compatible with the Triever Catheter's side port connector to establish an airtight seal. (Figure 3.4).

Figure 3.4: Triever Catheter Accessories and Model Dimensions

Model Number	Catheter Outer Diameter	Catheter Inner Diameter	Usable Length
25-101	16 Fr (5.3 mm)	13 Fr (4.5 mm)	113 cm
20-101	20 Fr (6.5 mm)	17 Fr (5.6 mm)	90 cm
22-101	24 Fr (7.6 mm)	21 Fr (6.9 mm)	90 cm

FLARE-FT2 Study Protocol 21-001

# 2.5 INDICATIONS FOR USE

Under US Regulations 510(k) number K201541, the FlowTriever2 Catheter is indicated for:

- The non-surgical removal of emboli and thrombi from peripheral blood vessels.
- Injection, infusion, and/or aspiration of contrast media and other fluids into or from a blood vessel.

The FlowTriever2 Catheter is intended for use in the peripheral vasculature.

The FLARE-FT2 study is an IDE confirmatory study evaluating the FlowTriever2 Catheter for the treatment of pulmonary embolism.

At present, the FlowTriever2 Catheter is not cleared for the specific indication for which it is being tested (e.g., treatment of pulmonary embolism) and, thus, is not commercially available for this indication. The FlowTriever2 Catheter used to treat PE will be under clinical investigation at sites where the responsible Institutional Review Board (IRB) has approved the FlowTriever Pulmonary Embolectomy Clinical Study-FlowTriever2 (FLARE-FT2) protocol.

Neither Inari Medical nor the Investigator may represent the investigational device as safe or effective for the purpose for which it is under clinical study or otherwise promote the product for this indication.

### 3 PRIOR INVESTIGATIONS

The FlowTriever System was first evaluated in a US pivotal Investigational Device Exemption trial, the FlowTriever Clinical Embolectomy Clinical Study (FLARE) study, in subjects with submassive (i.e., intermediate-risk) PE. The study was a prospective, multicenter study to evaluate the safety and effectiveness of the FlowTriever System in subjects eligible for endovascular treatment of acute PE. The FLARE study was completed in 2017 and resulted in the FlowTriever System cleared indication for use in the peripheral vascular and for the treatment of PE.

Following this FDA clearance, a subsequent post-market registry (FlowTriever All-Comer Registry for Patient Safety and Hemodynamics (FLASH)) was initiated to continue to evaluate the safety and effectiveness of the FlowTriever System for use in the removal of emboli from the pulmonary arteries in a real-world patient population. The all-comer nature of the registry allows for the evaluation of FlowTriever outcomes in a real-world population including both intermediate-risk and high-risk PE patients, and enrollment in the study is ongoing.

### 3.1 FLARE STUDY

The FLARE study, IDE # G160002, was a prospective, single-arm, multicenter study conducted at 18 sites across the United States from April 2016 to November 2017. The study evaluated the treatment of 106 patients with intermediate risk PE using the FlowTriever System. The study met both of its primary endpoints, which demonstrated safety and effectiveness and represented a successful treatment of PE. Data from the study supported FDA 510(k) clearance (K180466) for the FlowTriever System.

All patients enrolled in the study were symptomatic for 14 days or less, with clinical signs and presentation consistent with PE, including documented proximal PE by computed tomography, or CT, angiography, and a site-reported right ventricle/left ventricle, or RV/LV, ratio of 0.9 or greater by CT.

The primary effectiveness endpoint was a reduction in core laboratory-assessed RV/LV ratio. The average RV/LV ratio decreased from 1.53 (n = 104) at baseline assessment to 1.15 (n = 101) in the 48 hours after treatment using the FlowTriever, representing a statistically significant reduction in RV/LV ratio of 0.38 on average (25.1%; p < 0.0001).

The primary safety endpoint was measured by device-related death, major bleeding, treatment-related clinical deterioration, pulmonary vascular injury or cardiac injury in the 48 hours after treatment using the FlowTriever. Four patients (3.8%) experienced six major adverse events in the 48 hours after treatment. All major adverse events were determined to be procedure related, with no device-related major adverse events. All four (3.8%) patients exhibited clinical deterioration. There was one major bleeding event (0.9%) and one pulmonary vascular injury. The major bleeding event experienced by one patient was also classified as a pulmonary vascular injury and as clinical deterioration.

Two patients (1.9%) experienced respiratory deterioration during or immediately after the procedure that required emergent intubation. One patient (0.9%) became agitated during the procedure, requiring increased sedation, and had a ventricular fibrillation event that required cardioversion and emergent intubation. An additional 10 patients experienced serious adverse events within 30 days after treatment, none of which were determined to be procedure- or device-related. In total, 14 patients (13.2%) experienced 26 serious adverse events within 30 days, with five patients (4.7%) experiencing multiple serious adverse events. One patient (0.9%) died within 30 days of treatment because of respiratory failure from undiagnosed metastatic breast cancer.

FLARE Study results were published in Tu T, et al. A Prospective, Single-Arm, Multicenter Trial of Catheter-Directed Mechanical Thrombectomy for Intermediate-Risk Acute Pulmonary Embolism: The FLARE Study. JACC Cardiovasc Interv 2019.

**CONFIDENTIAL** Page 21 of 60 FLARE-FT2 Study

Inari Medical Version 4.0 FlowTriever2 Catheter 11-Aug-2023

### 3.2 FLARE STUDY RESULTS

A total of 106 subjects that met the eligibility criteria were consecutively enrolled and treated with the FlowTriever System comprising the full Intent-To-Treat ("ITT") population. Of these 106 subjects, two (2) subjects received thrombolytics during their index procedure and were therefore not included in the modified Intent-To-Treat (mITT) population. The mITT population was defined as all subjects in the "ITT Population" with no thrombolytics administered during the operative procedure. The primary effectiveness and safety analyses were done using the mITT population.

The disposition of subjects in the FLARE trial is depicted in **Figure 4**. In all, 106 subjects were enrolled and treated with the study device; 104 without thrombolytics. Among these, 101 had evaluable CTPA studies suitable for the primary effectiveness endpoint. There were also 101 subjects that had 48-hour data suitable for the primary safety endpoint. The mean baseline RV/LV ratio was  $1.5 \pm 0.4$ , and the mean 48-hour RV/LV ratio was  $1.2 \pm 0.3$ . Three subjects had missing values for the primary effectiveness endpoint at the 48-hour visit resulting in 101 subjects with both a pre-and post-RV/LV ratio for comparison. For these paired subjects, the mean change (reduction) in RV/LV ratio from pre- to post- was  $0.38 \pm 0.3$ , with a range from an increase of 0.4 to a decrease of 1.4. This mean change in RV/LV ratio was  $0.38 \pm 0.0001$ , indicating that the null hypothesis was rejected and the FlowTriever device met the performance goal.a

[figure not shown]

Figure 4. Disposition of Subjects in the FLARE Trial

For the primary safety endpoint, 4 subjects (3.8%) in the mITT population experienced one or more MAEs. The composite endpoint of 3.8% was statistically lower than the performance goal of 25% (p-value <0.0001), with an upper one-sided 95% confidence limit of 8.6%. The upper one-sided 95% confidence limit for the ITT population was 8.4%, which was significantly less than the performance goal of 25%.

In summary, the FLARE trial met its primary safety and effectiveness endpoints. This trial was the basis for the US FDA 510(k) clearance of the device in May 2018.

\_

\*Subject who did not meet eligibility requirement died during follow-up period.

<sup>a The p-value is from a one-sided t-test (Wald statistic) from the multiple imputation analysis, testing the null hypothesis that the mean change is not greater than the performance goal of 0.12.

#### 3.3 **DESIGN OF THE FLASH STUDY**

The primary study objective of FLASH is to evaluate the safety and effectiveness of the next-generation FlowTriever System for use in the removal of emboli from the pulmonary arteries in the treatment of acute pulmonary embolism (PE). The use of the device is being assessed in a real-world population, with eligibility criteria that closely approximate its use in clinical practice.

The FLASH Study is a prospective, single-arm, multicenter all-comer registry of the FlowTriever System for intermediaterisk (submassive) and high-risk (massive) PE. While originally designed to enroll up to 500 subjects at up to 50 registry sites in the United States, the study has been expanded to enroll up to 1,000 subjects treated with FlowTriever, including up to 800 subjects in up to 70 US sites and up to 200 in up to 30 Europe sites. The study will also include an additional 300 subjects with anticoagulation treatment as the initial planned primary treatment strategy for intermediate-risk PE. Enrollment in the FLASH registry is ongoing.

The primary endpoint is the rate of Major Adverse Events (MAE). MAEs are defined as a composite, when one or more of the following events occur:

- Device-related mortality through 48 hours after the index procedure, or
- Major bleeding through 48 hours after the index procedure, or
- Intra-procedural device or procedure-related adverse events, including:
  - Clinic deterioration defined by hemodynamic or respiratory worsening, or
  - Device-related pulmonary vascular injury, or
  - Device-related cardiac injury

Secondary safety endpoints include individual components of the MAE composite endpoint, major access-site complications requiring open surgical or endovascular intervention or blood transfusion, all-cause mortality through 30 days, and device-related serious adverse events within 30 days. Secondary effectiveness endpoints include reduction in pulmonary artery pressure (PAP) and other hemodynamic improvements during the procedure, and reduction in RV/LV ratio from baseline to 30 days and 6 months.

#### 3.4 FLASH INTERIM STUDY RESULTS

An interim analysis of outcomes out to 30 days on the first 250 subjects was recently published. 63 These subjects (60.9 ± 13.9 years, 52.4% male) were enrolled across 19 sites, with 93.2% having intermediate-risk PE and 6.8% high-risk PE. The average baseline RV/LV ratio was 1.5 ± 0.5 and sPESI was 1.6 ± 1.1. Elevated biomarkers were present in 96.2% of subjects, and 68.4% of subjects had concomitant DVT. The primary endpoint of composite MAEs occurred in three (1.2%) subjects, all of which were non-ICH major bleeds, and no deaths (0.0%) occurred within 48 hours.

In-hospital outcomes demonstrated significant improvements across several acute parameters. Subjects experienced significant on-table hemodynamic improvements, including a 22.2% decrease in mean pulmonary artery pressure (31.9 mmHg to 24.8 mmHg, P < 0.001) and a 13.3% increase in cardiac index in subjects with a low baseline cardiac index (1.7 to  $1.9 \text{ l/min/m}^2$ , P = 0.005). There was only one (0.4%) access site complication. The median post-procedure hospital length of stay was 3.0[2.0 - 5.0] days and ICU length of stay was 0.0[0.0 - 1.0] days.

Thirty day follow up data was available for 242 subjects in this analysis. In this population, there was one death (0.4% allcause mortality), which was unrelated to the device, and there were 13 hospital readmissions, only one of which was related to the patient's acute PE. The average RV/LV ratio improved by 28.3% at follow up (P < 0.001) and subjects with confirmed baseline dyspnea had a significant improvement from baseline to 30 days (Modified Medical Research Council Dyspnea Scale,  $2.9 \pm 1.1$  to  $0.8 \pm 1.1$ , P < 0.001).

**CONFIDENTIAL** Page 23 of 60 FLARE-FT2 Study

These interim results of the FLASH all-comer registry demonstrate both safety and efficacy of the FlowTriever System, with a low all-cause mortality rate (0.0% at 48 hours, 0.4% at 30 days; no device-related deaths), along with significant and immediate hemodynamic improvements and continued improvements in RV/LV ratio and dyspnea out to 30 days.

# 4 FLARE-FT2 STUDY OBJECTIVES

The FlowTriever2 Catheter is a catheter-based mechanical thrombectomy device for percutaneous endovascular retrieval of emboli from vasculature and is intended for use in the peripheral vasculature. The FlowTriever2 Catheter is designed to mechanically remove emboli and restore blood flow through the pulmonary arteries in patients experiencing PE.

# 4.1 PRIMARY ENDPOINT - EFFECTIVENESS

The study's primary effectiveness endpoint is the change in mean pulmonary arterial pressure from baseline pre-procedure to post-procedure.

# 4.2 PRIMARY ENDPOINT - SAFETY

The study's primary safety endpoint is incidence of adjudicated Serious Adverse Events (SAE), which is a composite of:

- Mortality through 48 hours after the index procedure related to FlowTriever2 Catheter
- Major bleeding through 48 hours after the index procedure related to FlowTriever2 Catheter
- Intra-procedural device or procedure-related adverse events, including:
  - Clinical deterioration defined by hemodynamic or respiratory worsening
  - Pulmonary vascular injury related to FlowTriever2 Catheter
  - Cardiac injury related to FlowTriever2 Catheter

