## 8.4 EVENT RELATIONSHIP

The Investigator will categorize the relationship of the adverse event as follows:

- **Study Disease-related:** Event is clearly attributable to underlying disease state with no temporal relationship to the device, treatment or medication.
- **Concomitant Disease-related:** Event is attributable to disease other than the study disease with no temporal relationship to the device, treatment or medication.
- **Procedure-related:** Event has a strong temporal relationship to the procedure or treatment with the device deployment or any user handling.
- **Device-related:** Event has a strong temporal relationship to the device and alternative etiology is less likely.
  - Primary Study Device: FlowTriever2 Catheter

FLARE-FT2 Study CONFIDENTIAL Page 41 of 60

- Ancillary Device: Any device other than the FlowTriever2 Catheter, such as the Triever Catheter, a
  guidewire, pressure monitoring catheter, or infusion catheter
- o **Device Unknown:** Device-related but unable to attribute a specific device relationship
- **tPA-related:** Event is clearly attributable to tPA medication with no temporal relationship to the device or treatment.
- Unrelated to the above categories: Event has no relationship to any of the above-mentioned categories.
- **Unknown:** Event relationship is not known or unsure.

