## 9 STATISTICS & DATA ANALYSIS

#### 9.1 SAMPLE SIZE CALCULATIONS

The sample size of 50 subjects reflects sample size to confirm the FlowTriever2 Catheter performance. The sample size of 50 subjects was estimated in order to provide at least 80% power with one-sided alpha = 0.05 for assuming FT2 safety event proportions of 11% vs. the performance goal of 25% from FLARE. Sensitivity analysis for this confirmatory study will be performed on a sub-population of the 50 subjects that did not receive adjunctive thrombolytics. Descriptive statistics on safety and effectiveness will be provided for all patients.

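### The primary safety composite has two conflicting attribution rules, and the main one omits major bleeds, deaths and injuries not tied to FlowTriever2 unless the subject also had clinical deterioration

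*Protocol*

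**What the plan says.** Protocol 4.2 defines the primary safety composite. Four of its five components carry an attribution limit to the investigational catheter alone: "Mortality through 48 hours after the index procedure related to FlowTriever2 Catheter", "Major bleeding through 48 hours after the index procedure related to FlowTriever2 Catheter", "Pulmonary vascular injury related to FlowTriever2 Catheter", and cardiac injury in the same form. The two injury components sit under a parent line that speaks of device or procedure relation. The fifth component, clinical deterioration, has no such limit, and Protocol 12 defines it as treatment-related. Protocol 9.3 and SAP 2.1 repeat this wording.

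SAP 5.2, which states the analysis, describes death and major bleeding as device-related and the intra-procedural events as device- or procedure-related, with no mention of FlowTriever2.

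Protocol 8.4 makes these different things. Its device-related category has three sub-classes: the primary study device (FlowTriever2), an ancillary class, "Ancillary Device: Any device other than the FlowTriever2 Catheter, such as the Triever Catheter", and an unknown-device class. Procedure-related is a separate category.

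The Triever Catheter is part of every FlowTriever2 treatment. In Protocol 2.2, "the FlowTriever2 Catheter is placed over the guidewire, through the Triever Catheter, and is passed through the clot", and Protocol 6.2.2 calls for a Triever20 or Triever24.

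On the predecessors, Protocol 3.1 says of FLARE: "All major adverse events were determined to be procedure related, with no device-related major adverse events". Protocol 3.3 gives the FLASH bleeding component as "Major bleeding through 48 hours after the index procedure, or", with no relatedness condition. Protocol 9.1 sizes the trial against "the performance goal of 25% from FLARE".

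**The concern.** There are two problems. First, the main definition and the analysis section do not select the same events, so the numerator of the primary safety rate is not fixed in advance. Second, the main definition is narrow for a device that is never used alone. A major bleed at the access site 12 hours after treatment could reasonably be coded to the large-bore Triever Catheter or to the procedure, and then would not meet the bleeding component.

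Effectiveness is not split this way: Protocol 6.1.4 takes pressure before the FlowTriever part of the procedure and again once the whole system is out.

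At stake is whether the reported rate describes what happens to patients treated with FlowTriever2, and whether it can be set beside the FLARE goal and the FLASH result. A low rate might partly reflect the attribution rule.

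**Working it through.** **1. The plan's own figures.** Inputs from Protocol 9.1 and SAP 5.1: n = 50, assumed rate 11%, goal 25%, one-sided alpha 0.05. With X binomial(50, p), the largest c with P(X ≤ c | 0.25) ≤ 0.05 is c = 7: P(X ≤ 7 | 0.25) = 0.0453, against 0.0916 at c = 8. Power is P(X ≤ 7 | 0.11) = 0.821, so the stated figure of at least 80% reproduces. The exact one-sided 95% upper limits for FLARE also reproduce: 4/104 gives 8.6% and 4/106 gives 8.4%, as in Protocol 3.2.

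**2. The two rules side by side**, for events in a subject without clinical deterioration:

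| Event and Protocol 8.4 class | Protocol 4.2/9.3, SAP 2.1 | SAP 5.2 |
|---|---|---|
| Post-procedural death or major bleed within 48 h, FlowTriever2 | counts | counts |
| Same, Triever Catheter (ancillary) | does not count | counts |
| Same, unknown device | does not count | counts |
| Same, procedure only | does not count | does not count |
| Intra-procedural injury, procedure only | not by its sub-bullet, although the parent line admits it | counts |

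If the subject also meets intra-procedural clinical deterioration (for example unplanned intubation or resuscitation), the subject counts in the composite under either rule.

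**3. FLARE (Protocol 3.1, 3.2).** Four subjects had six events: 4 deteriorations + 1 major bleed + 1 pulmonary vascular injury = 6. None was device-related. Under FlowTriever2-only wording, the bleed and the injury (2 of 6 events) would fail their own components. The endpoint counts subjects, however, and all four had deterioration, so the subject count could remain as high as 4/104 = 3.8% if each deterioration was judged intra-procedural. Had every component required device relation, it would have been 0/104 (upper limit 2.8%). The result therefore lies between 0 and 4, depending on the timing judgement.

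**4. FLASH (Protocol 3.3, 3.4).** 3/250 = 1.2%, all major bleeds. Relatedness is not reported, so under FlowTriever2-only wording between 0 and 3 would meet the bleeding component, giving 0% to 1.2%.

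**5. This trial.** One subject is 1/50 = 2 percentage points. As an illustration only, suppose the event rate over all attributions is 25% and a share s of those events is counted. The documents give no value for s. The chance of seeing at most 7 counted events is P(X ≤ 7 | 50, 0.25 × s):

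| s | Counted rate | Chance of ≤ 7 in 50 |
|---|---|---|
| 1 | 25% | 4.5% |
| 0.9 | 22.5% | 9.8% |
| 0.75 | 18.75% | 25.5% |
| 0.5 | 12.5% | 71.7% |
| 0.25 | 6.25% | 98.8% |

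This shows how far a comparison with 25% depends on matching definitions. It is not an error rate of the trial, which makes no formal test.

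**The case against.** The case for the present wording has substance.

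- The FlowTriever System already had a PE indication after FLARE, and this IDE study concerns FlowTriever2. Attributing safety to that catheter answers the study's question. This stands as a reason to report the FlowTriever2-only rate. It does not settle which rule is primary while SAP 5.2 says something else. With no comparator, isolating the catheter rests wholly on attribution, and Protocol 8.4 itself expects device events that cannot be assigned.
- Some attribution limits are inherited. Death was device-related in both FLARE and FLASH, and both injuries were device-related in FLASH. This stands: for those components the change is only from device to FlowTriever2. The limit on bleeding is new relative to FLASH, and in FLARE a procedure-related bleed and vascular injury were counted.
- SAP 5.2 may be shorthand for SAP 2.1. Possibly, but device-related is a defined category in Protocol 8.4 with three sub-classes, so the shorthand changes the count.
- Protocol 8.4 does not say that its codes are mutually exclusive, so an event might be both procedure- and FlowTriever2-related. The parent line for intra-procedural events is also worded as non-exhaustive. Both points soften the loss, but they leave it to interpretation.
- Secondary endpoints recover part: all-cause mortality and device-related SAEs to the 30-day visit, the latter including Triever and unknown-device events if read by Protocol 8.4. No named endpoint recovers a post-procedural, procedure-related major bleed, or a procedure-related injury without deterioration if the injury sub-bullets govern.

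A reader might infer that all Triever-, procedure- and unknown-device harms disappear from primary safety. The documents do not support that: clinical deterioration has no FlowTriever2 limit, and SAP 5.2 admits the wider device class.

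**Conclusion.** The primary safety composite needs correction on two counts: its definition and its analysis section conflict, and the FlowTriever2-only version leaves a specific gap. The gap is deaths and major bleeds after the procedure but within 48 hours that are not tied to FlowTriever2, and bleeds or injuries not tied to it in subjects without intra-procedural deterioration. The mismatch with the predecessors is clearest for major bleeding.

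The size is 2 percentage points per subject lost. How many would be lost cannot be derived from the documents; FLARE and FLASH both allow anything from no change to all counted events. So the rate may be understated, but that it will be is not shown.

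A reader might also infer an inflated type I error against the 25% goal. SAP 2 makes the endpoints descriptive with no role in deciding success, and SAP 5.1 relies on no hypothesis test. The 25% goal serves only to justify n = 50, and that calculation reproduces. The consequence is a rate that is not like-for-like with FLARE. This conclusion assumes that relatedness is assigned by the Protocol 8.4 classes, with Clinical Events Committee (CEC) adjudication overruling the investigator, as Protocol 8.7 states.

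**What to change.** Reconcile Protocol 4.2 and 9.3 (and the synopsis) with SAP 2.1 and 5.2 so that all state one attribution rule, and make the injury sub-bullets agree with their parent line.

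In SAP 5.2, report two versions of the 48-hour composite side by side: FlowTriever2-only, and events that the CEC relates to any FlowTriever System component (FlowTriever2, Triever, unknown device) or to the procedure. Add counts by Protocol 8.4 class, and state whether more than one class may be assigned to an event. For any comparison with FLARE or FLASH, use the version closest to that study's definition.

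This does not require replacing the primary definition with one that counts procedure-related deaths. That would go beyond both predecessors and is a trade-off for the sponsor.

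The cost is wording in two documents and one extra table. No new data are needed, since the relatedness codes and CEC adjudication are already planned, and n = 50 and its 82% power are unchanged if 11% and 25% are kept. The wider rate may look less favourable.
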